The PK data and MD data handling will be confirmed during blinded data review (BDR). PK data and MD data that are considered "invalid" will be flagged in the listing. Due to the nature of PK data and MD data, some issues may only be discovered after PK data and MD data are unblinded. Should new issues be identified post unblinding, and new data handling rules would have to be applied, a separate PK data and MD data handling document will be produced to provide detailed rationale and decision making. If there is clear evidence that PK sample handling errors, MD handling errors, or other factors are identified after data unblinding and these errors have led to unexpected erroneous data, then these erroneous data will be regarded as "invalid", full explanations will be given in the PK data and MD data handling document.

7.2 Analysis Visit Definitions

Table 3 Analysis Visit Window for PtGA, PhGA, mRSS, FVC, DLco, HAQ-DI

Visit Number	Analysis Visit	Nominal day	Analysis Visit Window
1	Screening	NA	NA to -1
2	Baseline	First dose day	NA
3	Week 2	Day 15	Day 2 to 29
4	Week 6	Day 43	Day 30 to 77
5	Week 16	Day 113	Day 78 to 147
6	Week 26	Day 183	Day 148 to 228
7	Week 39	Day 274	Day 229 to 319
8	Week 52 (EOT)	Day 365	Day 320 to 379
10	Week 56 (EOS/FU)	Day 393	Day 380 to 400

Table 3 Analysis Visit Window for other than PtGA, PhGA, mRSS, FVC, DLco, HAQ-DI and pregnancy test

Visit Number	Analysis Visit	Nominal day	Analysis Visit Window
1	Screening	NA	NA to -1

2	Baseline	First dose day	NA
3	Week 2	Day 15	Day 2 to 29
4	Week 6	Day 43	Day 30 to 77
5	Week 16	Day 113	Day 78 to 147
6	Week 26	Day 183	Day 148 to 228
7	Week 39	Day 274	Day 229 to 319
8	Week 52 (EOT)	Day 365	Day 320 to 379
9	Early termination (ET)	End of treatment	End of treatment + 7
10	Week 56 (EOS/FU)	Day 393	Day 380 to 400

Table 4 Analysis Visit Window for pregnancy test

Visit Number	Analysis Visit	Nominal day	Analysis Visit Window
1	Screening	NA	NA to -1
2	Baseline	First dose day	NA
3	Week 2	Day 15	Day 2 to 29
4	Week 6	Day 43	Day 30 to 77
5	Week 16	Day 113	Day 78 to 147
6	Week 26	Day 183	Day 148 to 204
	Week 32	Day 225	Day 205 to 249
7	Week 39	Day 274	Day 250 to 294
	Week 45	Day 316	Day 295 to 340
8	Week 52 (EOT)	Day 365	Day 341 to 379
9	Early termination (ET)	End of treatment	End of treatment + 7
10	Week 56 (EOS/FU)	Day 393	Day 380 to 400

The date of the first dose of study drug is defined as Day 1.

Unless otherwise specified, the baseline value will be the last observed value of the parameter of interest prior to the first intake of study drug (this includes unscheduled visits). For FVC, %pFVC and %pDLco etc in the pulmonary function test, the baseline value will be the last observed value prior to the first intake of study drug. The data of "accepted" or "failed" generated by the centralized over read specialist will be utilized for each pulmonary function test parameters. The data accepted by the centralized over read specialist will be used if it

exists. However, when there is no accepted data available at a visit, the failed data that will be approved in BDRM will also be used.

Unless otherwise specified, no data imputation will be performed using data from outside the allowable range.

For other visits, if there are multiple data in a window, the closest data to nominal day will be used. If the distance to the nominal day is the same, the data of later date will be used.

In the event that in a post baseline visit window there are only values from unscheduled visit, these values will be used to derive the value for this visit.

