11.5 Pulmonary Function Test

Pulmonary function tests (PFTs) are a group of tests that measure how well the lungs are performing. The test includes how well the subject is able to breathe and how effective the lungs are able to bring oxygen to the rest of the body. PFTs will include [REDACTED] and FVC.

Details of PFTs are described in full in a separate document (provided by the central PFT vendor) and will be in accordance with the American Thoracic Society/European Respiratory Society (ATS/ERS) Consensus Statement. Sites will receive centralized systems to perform spirometry tests (provided by a central PFT vendor) that will be in accordance with the study requirements and with ATS/ERS guidelines. Sites will perform [REDACTED] using their own equipment but will be required to enter the data into the system provided by the central PFT vendor.

PFT evaluators need to be trained and appropriately qualified to perform both Spirometry and [REDACTED] FVC measurements will be conducted in the clinical site at around the same time of day where possible with the subject in a sitting upright position. Subjects should undertake at least 3 attempts to generate acceptable and reproducible FVC data per ATS/ERS guidelines. The highest acceptable value will be selected following quality review by a centralized over read specialist in agreement with the site Investigator.

[REDACTED]. At least 2 acceptable tests that meet repeatability criteria will be performed. The best value (mean from acceptable values) will be selected following quality review by a centralized over read specialist in agreement with the site Investigator.

The acceptability of the FVC and [REDACTED] data will be determined by a centralized over read specialist. The centralized over read specialist will state whether a session has been accepted (passed QA) or rejected (failed QA). If rejected, the FVC measurements at screening and from Week 16 onwards should be repeated within 2 weeks. Only one repeat visit is required. The

clinical site should confirm that FVC is acceptable at screening visit before subjects are randomized.

Abnormalities of clinical significance will be reported as AEs.

If a subject's medical condition is worsening such as %pFVC decline, and at the Investigator's discretion, an HRCT scan may be performed as a part of standard of care based on local guidance to confirm worsening.

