15.5 The Impact of COVID-19

Since study subjects may not be able to come to the clinical site for protocol-specified visits, specific information on COVID-19 will be captured via eCRFs to explain the missed protocol-specified information due to COVID-19.

If any study procedures are deemed unsafe or in need of special precautions to safeguard the subject or others from the transmission of COVID 19, these will be documented in the TMF, and, if altered in any way relevant to data collection or interpretation, or statistical analysis, will be addressed in the final SAP.

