FVC measurements will be conducted in the clinical site at around the same time of day where possible with the subject in a sitting upright position. Subjects should undertake at least 3 attempts to generate acceptable and reproducible FVC data per ATS/ERS guidelines. The highest acceptable value will be selected following quality review by a centralized over read specialist in agreement with the site Investigator. Single-breath DLco will be performed at selected sites/countries in accordance with recently published ATS/ERS (the American Thoracic Society/European Respiratory Society) guidelines using equipment and testing techniques that meet ATS/ERS requirement. At least 2 acceptable tests that meet repeatability criteria will be performed. The best value (mean from acceptable values) will be selected by a centralized over read specialist in agreement with the site Investigator.

The acceptability of the FVC and DLco data will be determined by a centralized over read specialist. The centralized over read specialist will state whether a session has been accepted (passed QA) or rejected (failed QA). As the lungs are involved in most of dcSSc patients, there is some difficulties for dcSSc patient to repeat PFTs until they have acceptable values to meet the ATS/ERS criteria. Even if there was no accepted (passed QA) value at each visit, we accept that value as long as there is no issue with the flow loop legibility, since, for some dcSSc subjects, this is their best performance. Records of such manoeuvres should be retained since they may contain useful information. The QA passed values will be used at each visit unless there is no acceptable values at a visit.

PFTs data will include observed FVC, %predicted FVC, observed DLco, and %predicted DLco such as below.

- 1) Observed FVC is the best FVC and the highest FVC value from accepted values.
- 2) FEV is the forced expiratory volume in one second, which is the volume delivered in the first second of the best FVC manoeuvre..
- 3) %pFVC is the best FVC as a percentage of predicted FVC (Best FVC/pFVC x 100%).
- 4) Observed DLco is the best DLco uncorrected for Hb diffusing capacity of the lung for carbon monoxide in mLCO/min/mmHg.
- 5) %pDLco is the uncorrected best DLco as a percentage of corrected predicted DLco for hemoglobin (Best DLco/pDLco x 100%).

- Physician Global Assessment

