8.2.1 Primary Efficacy Endpoint

Primary Analysis

The primary treatment comparisons of interest are the ACR CRISS score for MT-7117 treatment group compared with placebo group at Week 52. MT-7117 treatment group includes all subjects treated with MT-7117 regardless down titrated or not. The treatment MT-7117 dose level at EOT will be compared with placebo as secondary analysis.

The primary endpoint will be summarized using descriptive statistics with interquartile range. The distribution of ACR CRISS score may not be normal distribution. For ACR CRISS score at Weeks 16, 26, 39, and 52 the comparison between MT-7117 treatment group and placebo group will be performed using the non-parametric analysis method. The point estimates and 2 sided 95% CIs and associated P-values for the difference between the treatment groups will be obtained using the Hodges-Lehman estimator corresponding to Wilcoxon's rank sum test. This non-parametric analysis will be performed with multiple imputation method, assuming missing at random. A supportive analysis will be performed at the same way for the primary endpoints using the per-protocol set (PPS). As a secondary analysis for the primary endpoint, the same analysis method will be applied to the intent to treat (ITT) population but the patients' data after taking rescue therapy will not be included. This approach will be performed to investigate a sensitivity for the primary analysis.

MI Step 1: The ACR CRISS score at week 52 will be multiply imputed using Fully Conditional Specification Method methodology under MAR assumption. The imputation for the missing ACR CRISS total score at week 52 will be conducted using all visit data of all subjects with available ACR CRISS total score up to week 52. The 50 different imputed datasets will be created using the MI procedure in SAS with 2023 for seed value. The following factors will be included in the imputation model: treatment group (TRT01P), randomization strata (the baseline autoantibody status of anti-RNA Polymerase III (positive or negative)).

[REDACTED]

[REDACTED]

[REDACTED]

[REDACTED]

[REDACTED]

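### The Week 52 FVC window closes at Day 379, so a protocol-compliant, accepted repeat of a rejected Week 52 FVC can fall outside it

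*SAP*

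**What the plan says.** **Windows.** SAP 7.2 has two tables numbered 3. The one for the CRISS components, "Table 3 Analysis Visit Window for PtGA, PhGA, mRSS, FVC, DLco, HAQ-DI", sets Week 52 at Day 320 to 379 (nominal Day 365) and Week 56 at Day 380 to 400 (nominal Day 393). Values outside a window are not carried in: "Unless otherwise specified, no data imputation will be performed using data from outside the allowable range". SAP 9.3 lists ACR CRISS, mRSS/%pFVC, SHAQ and the two global assessments at no visit after Week 52.

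**Repeat FVC.** The schedule of activities allows the Week 52 visit on Day 365 ± 7. Protocol 11.5 says of a session the central over-reader does not accept: "If rejected, the FVC measurements at screening and from Week 16 onwards should be repeated within 2 weeks".

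**Choice of FVC value.** SAP 7.2 prefers accepted data, but "when there is no accepted data available at a visit, the failed data that will be approved in BDRM will also be used". SAP 7.1.2.2 also tolerates a failed session, "Even if there was no accepted (passed QA) value at each visit, we accept that value", provided the flow loop is legible.

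**Missing score.** CRISS Step 2 needs all five component changes. For a missing score, SAP 8.2.1 says: "The ACR CRISS score at week 52 will be multiply imputed using Fully Conditional Specification Method methodology under MAR assumption".

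**Two softening texts.** The opening line of SAP section 7 lets BDRM decisions take precedence over the data rules. The note under the tables in SAP 9.3 mentions in passing that retests carry the same visit number.

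**The concern.** The protocol asks the site for a second FVC because the first failed central review. If the second one passes, it is the value the SAP wants for that visit. Yet the analysis window is shorter than the time the protocol allows to obtain it, and the days beyond the limit go to a visit with no planned CRISS analysis. The SAP's preference for accepted data is then defeated by its own date rule, at the visit that carries the primary endpoint. What is at stake for an affected subject is whether the primary score uses the accepted FVC, the rejected one, or an imputed value.

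**Working it through.** **1. The stated limit.** Day 379 is the midpoint of the neighbouring nominal days: (365 + 393)/2 = 379. The other upper limits follow the same rule to within a day: 29 (stated 29), 78 (77), 148 (147), 228.5 (228), 319.5 (319). The Week 56 row is thus what appears to fix the end of Week 52. This is an inference, but the arithmetic is exact.

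**2. Latest compliant repeat.** Nominal day + 7 (visit window) + 14 (repeat):

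| Visit | Latest repeat | Window ends | Inside? |
|---|---|---|---|
| Week 16 | 113 + 21 = 134 | 147 | yes |
| Week 26 | 183 + 21 = 204 | 228 | yes |
| Week 39 | 274 + 21 = 295 | 319 | yes |
| Week 52 | 365 + 21 = 386 | 379 | no, by 7 days |

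**3. How often.** Take the visit day v from 358 to 372 (15 days) and the repeat d = 1 to 14 days after the test, giving 15 × 14 = 210 combinations. The repeat is outside when v + d > 379. For v ≤ 365 this never happens. For v = 366, 367, ..., 372 it happens on 1, 2, ..., 7 of the 14 days. The total is 1 + 2 + ... + 7 = 28, and 28/210 = 13.3%. The other 182 stay inside.

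**4. Number of subjects.** The documents give no FVC rejection rate. Assume 5 to 30%, all 72 subjects reaching Week 52, and every rejected session repeated and then accepted:
- 5%: 72 × 0.05 × 0.133 = 0.48
- 10%: 0.96
- 20%: 1.92
- 30%: 2.88

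**5. Effect on one score.** The FVC coefficient in Step 2 is 0.21 per percentage point on the logit scale. For a hypothetical subject with mRSS −6, both globals −1, HAQ-DI −0.125 and an accepted FVC change of 0, the logit is −5.54 + 4.86 + 0.40 + 0.44 + 0.43 = 0.59, so CRISS = 0.64. If the rejected effort reads 4 points lower, the logit is 0.59 − 0.84 = −0.25 and CRISS = 0.44. The example sits near the 0.6 responder line by choice and shows only that a single score can move materially.

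**6. Effect on power.** With P(X>Y) = Φ(0.35/(0.5√2)) = 0.690, the Noether approximation gives power Φ(√(3N) × 0.190 − 1.96) = 79.6% at N = 72, which matches the plan's 80%. Losing 1 to 3 scores outright gives 79.1 to 77.9%.

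**7. After the change.** With Week 52 closing at Day 386, 0 of 210 combinations fall outside.

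**The case against.** The strongest reply is that the SAP already has the means to keep the repeat at Week 52. BDRM decisions can override the window rules, retests keep their visit number, and the FVC rule is worded by visit. This shows that displacement is not certain. It does not settle the matter. The visit-number remark sits in a note on what summary tables display, and nothing says that visit number prevails over the date window. Case-by-case decisions, even blinded ones, are weaker than a written rule for the primary endpoint.

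A second reply is that imputation is the less likely branch, because a failed but legible session is accepted. That stands. Imputation needs an unusable or unapproved first session as well as a repeat after Day 379. A third is that the power effect is small, which also stands.

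A reader might infer more than the documents support:
- **That Week 52 visits in general are lost.** No visit within the protocol's ± 7 days is affected, and visits on Day 373 to 379 are late but kept. Only a visit on Day 380 or later, at least 8 days beyond the protocol window, moves to Week 56, and it would lead to imputation rather than use of a rejected FVC. Protocol 15.5 foresees disruption ("Since study subjects may not be able to come to the clinical site for protocol-specified visits") but gives no rate of late visits.
- **That any FVC on Day 380 to 400 must belong to Week 52.** It could be the confirmatory %pFVC that CRISS Step 1 requires within a month, or another unscheduled test.
- **That the shorter window after Week 52 is itself an error.** It follows from the midpoint rule and a visit scheduled 28 days later.

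**Conclusion.** The point holds in a limited form. The date rule as written can set aside a protocol-compliant, accepted Week 52 FVC in favour of the rejected one or of imputation, and no text in the SAP clearly prevents it. The 13% exposure rests on uniform visit and repeat days and on the two weeks running from the test. Protocol 11.5 does not say when they start; if they start at the rejection notice, exposure is larger. The count of about 0.5 to 3 subjects also rests on the assumed rejection rate and on the completeness assumptions in the working. This does not threaten the trial's power, but it is a correctable gap in the rule for the primary endpoint.

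**What to change.** Before database lock, make two edits to SAP 7.2:

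1. Give FVC its own Week 52 window of Day 320 to 386. Start Week 56 at Day 387 for FVC, or drop the Week 56 row for it.
2. State that an accepted repeat of a rejected Week 52 FVC is Week 52 data and replaces the rejected value. This is needed as well as the wider window. The rule that picks the value nearest the nominal day would favour the earlier, rejected session, and the SAP does not rank that rule against its preference for accepted data. The statement also covers a repeat after Day 386 if the two weeks run from the rejection notice.

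The cost is a table edit and one sentence. The downside is that a few FVC values up to 386 − 365 = 21 days after nominal are used, possibly shortly after the last dose. Day 386 is also the first day of the Week 56 visit window (393 − 7), which is a further reason to tie the rule to the rejected session and not to the date alone.

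Extending all components to Day 400 is not required. Day 386 already covers every compliant repeat counted from the test, and the longer window would admit values up to 35 days after nominal, possibly off drug, to the primary endpoint.

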Record Adverse events	X	X	X	X	X	X	X	X	X	X	X		

Abbreviations: ACR CRISS = American College of Rheumatology Composite Response Index for Systemic Sclerosis; ECGG = electrocardiogram; EOS = End of treatment; KI-6 = Krbs von den Lungen-6; %nFVC = percent predicted forced vital capacity; %nPK = pharmacokinetic; PK = pharmacokinetic; SP-D =

Surfactant protein-D, [REDACTED]
receptor; SNPs= single-nucleotide polymorphisms, PhGA=Physician Global Assessment; PtGA=Patient Global Assessment; eCRF= electronic Case Report Form; HQ-DI= Health Assessment Questionnaire Disability Index; VAS= Visual Analog Scale

a. All subjects (completers and those who ET) will return to the clinical site 4 weeks after their last dose for a safety follow-up visit. For subjects who ET and will not revisit the clinical site, the site will perform a scheduled phone call for the collection of safety assessments (e.g., AEs, concomitant medication, and date of last dose of study drug).

b. A complete physical examination will be performed at Visit 1 and an abbreviated physical examination will be performed at all other specified time points.

c. Vital signs will include blood pressure, pulse rate, respiratory rate, and body temperature (e.g., oral, axillary or tympanic body temperature).

d. [REDACTED]

e. For female subjects of child-bearing potential, a serum pregnancy test will be performed at Visit 1, a urine pregnancy test (on-site) will be performed at all other site visits, and a urine dipstick pregnancy test at home or other home testing arrangements will be performed at Telephone Visits (Visit 6A and 7A).

f. Refer to Table 3 for laboratory evaluations.

g. ESR will be analyzed locally at the site level and at Screening only.

h. PK blood samples for MT-7117 will be collected at Visit 2 predose, Visits 3, 4, 5, 6, 7, and Visit 8 at any time during each visit. Date and time of study drug dose and date and time of PK sample collection will be recorded.

i. Blood samples will be collected for optional PGx analysis for those subjects who have provided informed consent.

j. [REDACTED]

SHAO is composed of HAO-DI and VAS

III.

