n. Nevi (Melanocytic Lesions) evaluation will be performed by a local dermatologist or qualified site staff. Baseline nevi (Melanocytic Lesions) evaluation will be performed at any time during the screening period before randomization at Visit 2 (Day 1). The nevi (Melanocytic Lesions) evaluation at Visit 9 is to assess for the reversibility if any suspicious nevi (Melanocytic Lesions) changes that were observed during treatment as per the Investigator's (and/or dermatologist's or other qualified site staff) judgment. Any follow-up will be recorded in the eCRF. Nevi (Melanocytic Lesions) assessment will be described in a separate document.

p. Subjects will be asked whether they believe they received active or placebo treatment.

q. Concomitant medications at screening, baseline, and used during study treatment will be reviewed, recorded and discussed with the Sponsor and medical Monitor (as needed).

r. [REDACTED]

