10.1.5 Safety Follow-up Period/End of Study

For all subjects who complete the double-blind treatment period, a safety follow-up visit will occur at Week 56 (Visit 9), 4 Weeks (± 7 days) after the last dose of study drug.

Any unresolved AE or SAE will be followed according to Section 14.9.

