9.3 Analysis Visits to Report

Efficacy:

Analysis Visit	Variables											
	ACR	Revised CRISS	mRSS / %pFVC	SH AQ	PTG A/ PHGA	[REDACTED]						
Screening			X								X	
Baseline			X		X		X	X	X			X
Week 2										X		
Week 6						X	X			X		
Week 16	X	X	X	X	X	X	X		X			

Week 26	X	X	X	X	X	X	X	X	X	X	X	X
Week 39	X	X	X	X	X	X	X		X	X	X	X
Week 52	X	X	X	X	X	X	X	X	X	X	X	X
Week 56 (EOS/FU)									X			

Safety:

Analysis Visit	Variables				
	Lab	Vital Signs	ECGs	Nevi	Physical exam
Screening	X	X	X	X	X
Baseline	X	X			X
Week 2	X	X		X	X
Week 6	X	X		X	X
Week 16	X	X			X
Week 26	X	X	X	X	X
Week 39	X	X			X
Week 52	X	X	X	X	X
Week 56 (EOS/FU)	X	X		X	X

Unscheduled visits, retests (same visit number assigned) and follow-up visits will not be displayed in by-visit summary tables, but will be included in the data listings.

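### SAP safety windows file an early terminator's off-drug follow-up under a Week 2 to Week 52 visit when the last dose is on or before Day 351

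*SAP*

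**What the plan says.** **Timing of the visit.** Protocol Table 1, footnote a, repeated in the SAP's schedule, says: "All subjects (completers and those who ET) will return to the clinical site 4 weeks after their last dose for a safety follow-up visit". Protocol 10.1.5 gives the tolerance for those who complete treatment: "a safety follow-up visit will occur at Week 56 (Visit 9), 4 Weeks (± 7 days) after the last dose of study drug". For nevi, the Table 1 footnote states a purpose: "The nevi (Melanocytic Lesions) evaluation at Visit 9 is to assess for the reversibility" of suspicious changes seen on treatment.

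**Filing of the data.** SAP 7.2 sets the origin: "The date of the first dose of study drug is defined as Day 1". The second Table 3, which covers labs, vital signs, physical examination and nevi, defines Week 2 to Week 56 by day ranges from that origin. Week 52 (EOT) is Day 320 to 379 and Week 56 (EOS/FU) is Day 380 to 400. The one row tied to stopping treatment is Early termination, whose window is "End of treatment + 7".

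**Choice within a window.** "if there are multiple data in a window, the closest data to nominal day will be used"; if two values are equally distant, the later one is taken.

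**Reporting.** The safety grid in SAP 9.3 has no ET row. It marks Week 56 (EOS/FU) for labs, vital signs, nevi and physical examination. The sentence below it says: "Unscheduled visits, retests (same visit number assigned) and follow-up visits will not be displayed in by-visit summary tables".

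**The concern.** The follow-up visit is anchored to last dose, and the window meant to hold it is anchored to first dose. The two agree for a subject who takes drug to Week 52. For someone who leaves the study earlier, the follow-up comes before Day 380. No rule sends it to EOS/FU, and none keeps it out of the treatment visits.

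An off-drug measurement can therefore be tabulated as Week 16, 26, 39 or 52, either in place of the ET value or in a visit the subject never attended. A laboratory value or nevus finding that has recovered after stopping would then look like an on-treatment result. The EOS/FU row would lack the subjects for whom reversibility is of most interest.

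**Working it through.** **Inputs.** Windows [a, b] with nominal day N, from the second Table 3 in SAP 7.2: Week 2 [2, 29], 15; Week 6 [30, 77], 43; Week 16 [78, 147], 113; Week 26 [148, 228], 183; Week 39 [229, 319], 274; Week 52 [320, 379], 365; Week 56 [380, 400], 393. L is the last-dose day, and the follow-up is on L + 28.

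**1. The plan's own figure.** Week 52 on Day 365 plus 28 days is Day 393, the SAP's nominal day for Week 56. The table is consistent for a completer.

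**2. Cut-off.** The follow-up is filed as a treatment visit when L + 28 ≤ 379, that is L ≤ 351. L = 352 gives Day 380, the first day of Week 56. If the ± 7 days is also allowed for early terminators, the limits are 379 − 35 = 344 (always misfiled) and 379 − 21 = 358 (possibly misfiled). The ET row cannot hold the visit, because even 21 days exceeds 7.

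**3. ET values compete in the day windows (ET on Day L).** Both values lie in one window when a ≤ L ≤ b − 28. The follow-up is selected when |L + 28 − N| ≤ |L − N|, that is L ≤ N − 14, with the tie going to the later date.

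| Window | b − 28 | N − 14 | Follow-up displaces ET value | Same window, on-drug value kept |
|---|---|---|---|---|
| Week 2 | 1 | 1 | none | none |
| Week 6 | 49 | 29 | none | 30–49 (20 days) |
| Week 16 | 119 | 99 | 78–99 (22) | 100–119 (20) |
| Week 26 | 200 | 169 | 148–169 (22) | 170–200 (31) |
| Week 39 | 291 | 260 | 229–260 (32) | 261–291 (31) |
| Week 52 | 351 | 351 | 320–351 (32) | none |
| Total | | | 108 | 102 |

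For L = 2–29, 50–77, 120–147, 201–228 and 292–319 (5 × 28 = 140 days) the follow-up falls in the next window and fills a visit that would otherwise be empty. Check: 108 + 102 + 140 = 350, the number of days from 2 to 351. With the follow-up at +21 or +35 days, the displacement count is 126 or 89.

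**4. ET values sit only in the ET row.** The follow-up then displaces no ET value. Assuming scheduled visits on nominal days, an attended scheduled visit is kept when N ≤ L ≤ b − 28: L = 43–49 (7), 113–119 (7), 183–200 (18) and 274–291 (18), 50 days in all. On the other 350 − 50 = 300 days the follow-up becomes the reported value for a treatment visit. The ET value appears in no by-visit table.

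**5. Examples, with ET competing.**
- Last dose Day 91, ET Day 94, follow-up Day 119. Distances from 113 are 19 and 6, so the follow-up becomes Week 16.
- Last dose and ET Day 330, follow-up Day 358. Distances from 365 are 35 and 7, so the follow-up becomes Week 52 (EOT), which the vital-sign shift table uses.

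**The case against.** The strongest defence is that little of consequence passes through these windows. TEAEs, hepatic AESIs and hyperpigmentation events are not assigned to visits. The liver thresholds in SAP 7.1.3.2 apply at any post-baseline time. Nevi of clinical concern are recorded as AEs (Protocol 12.4), and all safety data are listed. That stands and limits the scope to descriptive output.

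SAP 9.3 could also be read as dropping follow-up records from the by-visit tables. But it does not say that they are removed before windowing, and its own grid marks Week 56 as reported, so it does not settle the matter. Some early terminators will have only the telephone contact allowed by footnote a and so no measurements to misfile. That lowers the number affected but does not change the rule.

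Four stronger readings are tempting and not supported:
- **The follow-up generally overwrites the last on-drug value.** This needs ET values to compete in the day windows, which the SAP leaves open, and then holds only for some stop days.
- **Everyone who stops drug is affected.** Subjects who stop treatment but stay in the study are meant to attend scheduled visits through Week 52. Off-drug values at those visits are intended.
- **The EOS/FU window is too narrow for completers.** Adding the Week 52 tolerance to that in 10.1.5 gives 372 + 35 = Day 407. But Table 1 sets Visit 9 at Day 393 ± 7, or Day 386 to 400, all inside Day 380 to 400.
- **The distortion falls mainly on active.** Protocol 8.2.2 reports more discontinuations due to TEAEs at 300 mg in the EPP/XLP study, driven primarily by pigmentation, headache and gastrointestinal events. Transaminase elevations in the Phase 1 study cited in 8.2 were 6/36 and 2/12, 17% in each group. This trial also allows dose reduction. The direction by arm is not established.

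**Conclusion.** The windowing rule is wrong as written for subjects who terminate the study early. With follow-up at 28 days and last dose on or before Day 351, their off-drug safety follow-up is filed under a Week 2 to Week 52 visit. Whether it also displaces an ET value depends on a precedence rule the SAP does not give: 108 of 350 possible last-dose days if ET values compete, none if they do not. Under either reading off-drug values enter treatment rows.

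The day counts treat every stop day alike and are not proportions of the 72 subjects; no dropout rate is used. The outputs exposed are the by-visit lab, vital-sign, physical-examination and nevi summaries, the liver plots in SAP 8.3.2 and the vital-sign shift to EOT in 8.3.3. The ECG summaries are not exposed, since the 9.3 grid has no ECG at Week 56. This should be corrected before database lock, but it does not threaten the main safety conclusions.

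**What to change.** 1. In SAP 7.2, assign the Visit 9 safety follow-up of early terminators to EOS/FU by its timing relative to last dose (4 weeks ± 7 days), and exclude that visit from the Week 2 to Week 52 windows. Keep the scheduled visits of subjects who stop drug but remain in the study, flagged as off-drug. A blanket exclusion of all data after last dose would remove those visits too.
2. State whether the ET row takes precedence over an overlapping day window, and add ET to the visits reported in SAP 9.3.
3. Reconcile the 9.3 sentence on not displaying follow-up visits with the grid that marks Week 56.

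The cost is SAP wording and programming, with no change to data collection. Some later by-visit rows will contain slightly fewer values.
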